7. ENDPOINTS

Primary Endpoint

The primary endpoint is the composite risk of vessel-oriented composite endpoint (VOCE), including target vessel revascularization (TVR), vessel-related myocardial infarction (MI), and cardiovascular death.

Secondary Endpoint

- Individual components of the primary endpoint.
- Hospitalization for unstable angina.
- Angina status assessed using the Seattle Angina Questionnaire (SAQ). The SAQ will be used to evaluate patients' quality of life and the impact of angina symptoms over time. Scores from the main subscales (physical limitation, angina stability, angina frequency, treatment perception, and overall quality of life) will be analysed to correlate symptom severity with coronary physiology parameters (e.g., FFR/angiography-derived FFR).
- Number of prescribed antianginal drugs. The number of prescribed antianginal medications will be monitored to assess the intensity of pharmacological treatment required during follow-up. This parameter will serve as a proxy for residual disease severity and will allow comparison between patients managed conservatively and those treated with invasive interventions.

[figure not shown]

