10. STUDY DURATION

Recruitment: Once eligibility for the protocol is confirmed, informed consent is requested and obtained, and the patient is then enrolled in the study.

Patient involvement: Enrollment includes patients undergoing coronary angiography from January 2010 to December 2024.

Follow up: Follow-up will be maintained until all patients have completed a clinical evaluation at 10 years.

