12. STATISTICAL ANALYSIS

Continuous variables will be tested for normal distribution using the Kolmogorov-Smirnov test.

Variables with a normal distribution will be presented as mean \pm standard deviation and compared using t-tests and one-way ANOVA. Otherwise, median [interquartile range] will be used, and comparisons will be performed using the Mann-Whitney U and Kruskal-Wallis tests. Categorical variables will be summarized as absolute and relative frequencies (percentages) and compared using the χ^2 test. Correlations between variables will be evaluated using linear and logistic regression analyses. The level of statistical significance will be set at $\alpha = 0.05$. Kaplan-Meier curves will be plotted to describe event-free survival, and differences between groups will be tested using the log-rank test. The primary analysis will be based on events occurring during the entire follow-up period for each patient at database lock. Any confounding factors will be tested using Cox regression models. Variables with a p-value < 0.1 in univariate analysis will be included in a multivariate analysis to identify independent predictors. When appropriate, 95% confidence intervals will be calculated.

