The pathological correlate at the myocardial level is cardiomyocyte necrosis. A small proportion of patients may present with ongoing myocardial ischemia, characterized by one or more of the following: recurrent or ongoing chest pain, marked ST depression on 12-lead ECG, heart failure and hemodynamic or electrical instability. Due to the amount of myocardium in jeopardy and the risk of malignant ventricular arrhythmias, immediate coronary angiography and, if appropriate, revascularization are indicated. The clinical definition of MI denotes the presence of acute myocardial injury detected by abnormal cardiac biomarkers in the setting of evidence of acute myocardial ischaemia.

Any MI without a clearly identifiable culprit vessel is counted as target vessel related.

Cardiovascular death

Deaths are classified as cardiovascular, non-cardiovascular, or of undetermined cause according to ARC-2 criteria. Deaths of undetermined cause are classified as cardiovascular but as a separate subcategory of cardiovascular deaths to indicate this uncertainty. Deaths due to procedural complications or concomitant treatments are classified as cardiovascular. Only deaths due to a documented non-cardiovascular cause (e.g., cancer) are classified as non-cardiovascular. Cardiovascular deaths in patients with multivessel disease are assigned to each affected vessel.

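### Read as risks, the Kaplan-Meier curves over ten or more years censor competing deaths and overstate the cumulative incidence of VOCE, and relatively more that of TVR and MI, within the enrolled cohort

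*Protocol*

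**What the plan says.** - **Method.** Protocol Section 12: "Kaplan-Meier curves will be plotted to describe event-free survival", with groups compared by the log-rank test. For adjustment, "Any confounding factors will be tested using Cox regression models". No cumulative-incidence or competing-risk method is named.
- **Window.** Section 12 does not truncate: "The primary analysis will be based on events occurring during the entire follow-up period for each patient at database lock". Section 10 adds: "Follow-up will be maintained until all patients have completed a clinical evaluation at 10 years". Index procedures run from January 2010 to December 2024. If the last patient reaches 10 years at the end of 2034, the first will have almost 25 years.
- **Endpoints.** Section 7 defines VOCE as "including target vessel revascularization (TVR), vessel-related myocardial infarction (MI), and cardiovascular death". The first secondary endpoint is "Individual components of the primary endpoint".
- **Deaths.** Section 15: "Only deaths due to a documented non-cardiovascular cause (e.g., cancer) are classified as non-cardiovascular". Deaths of undetermined cause count as cardiovascular, so only documented non-cardiovascular deaths fall outside VOCE.
- **Enrolment.** The synopsis and Section 5 require written consent, sought after the index procedure. No route is described for including a patient who has already died.

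**The concern.** A patient who dies of cancer can no longer have a VOCE. A Kaplan-Meier curve of VOCE has no place for that death except censoring, which treats the patient as still able to have the event later. One minus the curve then estimates risk in a hypothetical population without non-cardiovascular death, not the proportion of patients who have a VOCE. For TVR alone or MI alone, cardiovascular death competes as well.

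Over one year this hardly matters. Over the 10 to 25 years that this protocol analyses, it can. The primary objective is a risk profile, and Section 11 plans subgroups by FFR severity, so readers will be inclined to take risks off the curves. Where non-cardiovascular mortality differs between strata, the inflation differs too.

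**Working it through.** The protocol gives no Kaplan-Meier or cumulative-incidence figure to reproduce, and no death rate. Every hazard below is an assumption.

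**Inputs.**
- VOCE hazard *a*: 3% to 6.45% per year, constant. The upper value implies a 12-month risk of 1 − exp(−0.0645) = 6.2%, within the 6.1% to 6.7% that Section 11 quotes from two other trials. Those are composite rates, not VOCE rates.
- Split of VOCE: TVR 50%, MI 25%, cardiovascular death 25%.
- Non-cardiovascular death *b*: 1% to 3% per year.

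**Step 1. All deaths observed from the index procedure.**

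1 − KM = 1 − exp(−*at*); cumulative incidence = *a*/(*a*+*b*) × [1 − exp(−(*a*+*b*)*t*)].

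- *a* = 0.03, *b* = 0.01, *t* = 10: 1 − exp(−0.30) = 25.9%, against 0.75 × [1 − exp(−0.40)] = 24.7%. Excess 1.2 points.
- *a* = 0.0645, *b* = 0.03, *t* = 10: 1 − exp(−0.645) = 47.5%, against 0.6825 × [1 − exp(−0.945)] = 41.7%. Excess 5.8 points.

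The 10-year range with full capture of deaths is therefore 1.2 to 5.8 points. At 1 year, with *b* = 2%, the gap is 0.1 point or less.

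**Step 2. Only patients alive at consent.** Deaths before consent never enter the data, so they cannot be censored. This was simulated with index dates uniform over 2010 to 2024, consent assumed at mid-2025, follow-up to the end of 2034 and time counted from the index procedure. One minus Kaplan-Meier was compared with Aalen-Johansen. The VOCE excess in percentage points, with *b* from 1% to 3%, was:

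| VOCE hazard | 10 years | 15 years | 20 years |
|---|---|---|---|
| 3%/yr | 0.2–0.7 | 0.7–2.2 | 1.6–4.5 |
| 6.45%/yr | 0.4–1.3 | 1.1–3.4 | 2.2–6.4 |

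Repeat runs move these by about 0.1 point (the 1.3 is 1.2 in some). In a middle case (*a* = 4%, *b* = 2%), one minus Kaplan-Meier against Aalen-Johansen is 28.3% against 27.8% at 10 years, 40.7% against 38.9% at 15, and 51.4% against 47.8% at 20.

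**Step 3. TVR and MI.** The competing hazard is now *b* plus the cardiovascular death hazard. In the middle case, at 10 years with full capture:

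| Endpoint | 1 − KM | Cumulative incidence | Excess (points) | Ratio |
|---|---|---|---|---|
| VOCE | 33.0% | 30.1% | 2.9 | 1.10 |
| TVR | 18.1% | 15.7% | 2.4 | 1.15 |
| MI | 9.5% | 8.2% | 1.3 | 1.15 |

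The ratio is larger for TVR and MI because cardiovascular death competes too. With non-cardiovascular death as the only competitor, the TVR ratio (1.100) is close to that of VOCE (1.096). In points, TVR and MI lie below VOCE here. Among patients alive at consent the ordering of the ratios is the same, at about 1.03 for TVR against 1.02 for VOCE.

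**The case against.** **The censoring rule is inferred, and an SAP could settle it.** This is true as far as it goes. Section 12 does not say that non-cardiovascular deaths are censored, and event-free survival could be read as counting every death. But on that reading the curve no longer shows the VOCE of Section 7. Kaplan-Meier is a named method, and an SAP that used cumulative incidence would depart from it. Either reading calls for the same clarification.

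**The protocol does not promise absolute risks by FFR stratum.** That also stands. The point is therefore conditional: it applies when the curves are read as risks.

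**Retrospective consent shrinks the effect.** This is the strongest objection, and it stands. A reader might take the full-capture figures (up to 5.8 points at 10 years) as the error in this registry. The documents do not support that, because pre-consent deaths are not in the data.

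**The registry's VOCE risk may be too low, not too high.** A reader might infer that VOCE will be overstated relative to all eligible patients. That does not follow. In the middle case the enrolled cohort's 10-year one minus Kaplan-Meier is 28.3%, below the 30.1% cumulative incidence in all eligible patients, because pre-consent cardiovascular deaths are lost. That is a separate bias, and it does not make Kaplan-Meier the right estimator. TVR differs: 18.1% in the enrolled cohort still exceeds 15.7% in all eligible patients.

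**The primary analysis is unaffected.** A reader might infer that the log-rank and Cox results are invalid. They are not: with competing deaths censored they compare cause-specific hazards, which suits a search for predictors.

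**Conclusion.** The point holds for absolute risks within the enrolled cohort. One minus Kaplan-Meier overstates the cumulative incidence of VOCE by about 0.2 to 1.3 points at 10 years, 0.7 to 3.4 at 15 and 1.6 to 6.4 at 20. These figures assume constant hazards, a quarter of VOCE being cardiovascular death, non-cardiovascular death at 1 to 3% per year, and consent at mid-2025. If pre-consent deaths were also captured, the 10-year excess would be about 1.2 to 5.8 points. For TVR and MI the overstatement is larger in relative terms only. The effect is modest at 10 years and grows over the untruncated follow-up that Section 12 specifies. It should be changed because the better estimator costs almost nothing, not because the primary inference fails.

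**What to change.** In Section 12:

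- Report VOCE as Aalen-Johansen cumulative incidence with non-cardiovascular death as the competing event.
- Report TVR and MI the same way, with any death not counted in that endpoint as the competing event.
- Keep the log-rank test and the Cox models, and describe them as cause-specific.
- Keep Kaplan-Meier only for endpoints that include all-cause death.

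The cost is a sentence or two and standard software. Section 15 already classifies deaths by cause, so no new data are needed. Reported risks will come out slightly lower. The loss of deaths before consent needs its own treatment; this change does not remove it.

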4. STUDY OBJECTIVES

Primary Objective

The primary objective is to identify a risk profile for vessel-oriented composite endpoint (VOCE) associated with the functional characteristics of coronary lesions documented during coronary angiography.

Secondary Objectives

Secondary objectives include:

- Assessing the prognostic value of physiological parameters (invasive FFR and angiography-derived FFR).
- Analysing the clinical, demographic, and angiographic characteristics of patients with coronary lesions evaluated by coronary physiology to identify high-risk subgroups.
- Investigating the correlation between coronary physiology values and angina symptoms.
- Comparing invasive FFR with angiography-derived FFR.
- Comparing clinical outcomes between patients managed conservatively and those undergoing invasive interventions.

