6. DESCRIPTION OF THE DISEASE IN THE STUDY

Ischemic Heart Disease and General Information on Coronary Angiography

The selection of eligible patients is based on the review of hospital registries and the analysis of coronary angiography procedures performed from January 2010 to December 2024.

Participants with suspected CAD undergo coronary angiography as part of the standard diagnostic and therapeutic pathway, in accordance with current guidelines for the management of ischemic heart disease. A patient is considered eligible if at least one mild or intermediate coronary stenosis is identified on angiographic assessment and subsequently evaluated with a coronary physiology test (fractional flow reserve [FFR] or angiography-derived FFR). These functional assessments guide the operator's decision to proceed with or defer vessel revascularization.

If a physiological evaluation of CAD is performed, the corresponding data — including FFR and/or angiography-derived FFR — are collected and recorded. The initial angiogram of all patients will be stored, anonymized, and kept locally for functional analysis (acceptable formats include CD, DVD, or digital files).

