8. PLANNED PROCEDURES AND DATA COLLECTION

The VR-CP study is a retrospective observational study enrolling consecutive patients who underwent coronary angiography for suspected ischemic heart disease and were found on angiographic examination to have coronary lesions evaluated using coronary physiology testing (FFR or angiography-derived FFR). These physiology assessments guided the decision to proceed with or defer target vessel revascularization.

Regardless of whether the lesion was treated invasively or managed conservatively, patients' clinical status and any adverse events are periodically recorded.

[figure not shown]
This retrospective follow-up is conducted through the collection of information from medical records, direct contact during outpatient visits, or via telephone communications, in order to ensure longitudinal data collection at 12-month intervals.

Fig. 1
Summary of Activities Performed

Flowchart

Fig.2 Retrospective Observational Study Design

*at the time of index procedure

DATA MANAGEMENT AND PROCEDURES TO ENSURE DATA CONFIDENTIALITY

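### Section 12's only stated entry rule for the multivariable Cox model, univariate p<0.1, can let a p-value decide whether the FFR-VOCE hazard ratio is routine-care risk or management-adjusted risk

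*Protocol*

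**What the plan says.** The statistical section gives a single entry criterion: "Variables with a p-value < 0.1 in univariate analysis will be included in a multivariate analysis to identify independent predictors". On confounding it adds only: "Any confounding factors will be tested using Cox regression models". It names no confounder and exempts no variable from the screen.

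The primary objective (Section 4) is to "identify a risk profile for vessel-oriented composite endpoint (VOCE) associated with the functional characteristics of coronary lesions". It does not say whether this means risk under physiology-guided care or risk at a given management. A secondary objective is "Comparing clinical outcomes between patients managed conservatively and those undergoing invasive interventions".

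Section 8 describes how exposure and treatment are linked: "These physiology assessments guided the decision to proceed with or defer target vessel revascularization". Section 6 says the same. Treated and deferred patients are followed together ("Regardless of whether the lesion was treated invasively or managed conservatively"). No section says whether index management is always in the FFR model, always out of it, or a stratifier.

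**The concern.** Management lies downstream of FFR. Leaving it out gives the risk that goes with an FFR value under the care patients actually received. Putting it in gives the association of FFR with VOCE at a given management. The choice between them should follow from the objective.

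Under the stated rule the choice may instead follow from the univariate p-value for management. In this design that p-value is a poor guide. If revascularisation lowers VOCE, treated vessels carry both higher underlying risk and a treatment benefit, so their crude event rate can look like that of deferred vessels although management matters. The same masking can weaken FFR in its own univariate test. At stake is the meaning of the main result for the primary objective and, less often, whether FFR is retained as a confounder in the management comparison.

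**Working it through.** The plan gives no figure for this point, so there is nothing to reproduce first. The check asks how often management would fail the screen, and how far the FFR HR moves when it does.

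**Event counts.** From Section 11, year one gives 1,000 × 0.061 = 61 to 1,200 × 0.067 = 80 events. Section 10 continues follow-up until all patients reach 10 years. Assume 1,100 patients, 70 events in year one and mean follow-up of 12.5 years. A later hazard h then adds 1,030 × (1 − exp(−11.5h)) events. The total is about 128 at 0.5% per year, 282 at 2% and 371 at 3%. So 120 events is a low extreme, and 360 and 550 are also examined.

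**Assumed inputs (not in the protocol).** FFR is normal with mean 0.82 and SD 0.08. Revascularisation is 90% at or below 0.80 and 5% above. The FFR HR is 1.3 per 0.05 lower at fixed management. There are 1,100 subjects with one target vessel each.

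**Step 1, separation of the groups.** The share at or below 0.80 is Φ(−0.25) = 0.401. The treated share is p = 0.9 × 0.401 + 0.05 × 0.599 = 0.391, so p(1−p) = 0.238. Mean FFR is 0.743 at or below the threshold and 0.872 above it. Mixing these gives 0.753 in treated and 0.863 in deferred vessels, a gap of d = 2.21 units of 0.05. Vessels managed contrary to the threshold: 0.05 × 0.599 × 1,100 = 33 treated above it and 0.10 × 0.401 × 1,100 = 44 deferred at or below it, 77 in all.

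**Step 2, univariate management effect.** log HR ≈ ln(treatment HR) + d × ln(1.3), and d × ln(1.3) = 2.21 × 0.262 = 0.58. At treatment HR 0.6 this is −0.51 + 0.58 = 0.07, a crude HR of about 1.07. At 0.8 it is −0.22 + 0.58 = 0.36, about 1.43.

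**Step 3, chance of failing p<0.1.** With D events, SE ≈ 1/√(0.238 D) and z = |log HR|/SE. The chance of failing is Φ(1.645 − z) − Φ(−1.645 − z).

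**Step 4, FFR HR without management.** log HR ≈ 0.262 + k × ln(treatment HR), where k = 0.238 × 2.21/(0.08/0.05)² = 0.205. At treatment HR 0.6: 0.262 − 0.105 = 0.157, HR 1.17. At 0.8: 0.262 − 0.046 = 0.216, HR 1.24.

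| Treatment HR | FFR HR without / with management | Management fails, formula | Management fails, simulation |
|---|---|---|---|
| 0.6 | 1.17 / 1.30 | 88%, 83%, 80% at 120, 360, 550 events | 84%, 85%, 82% |
| 0.8 | 1.24 / 1.30 | 40%, 5% at 120, 360 | 39%, 6% |
| 1.0 | 1.30 / 1.30 | 7%, 0% at 120, 360 | 7%, 0% |

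The simulations used exponential event times and Wald tests. They agree with the approximations.

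**Step 5, does selection mix the two quantities?** With FFR HR 1.4, treatment HR 0.6 and 360 events, management was kept in 64% of simulated studies. The mean FFR HR was 1.40 when it was kept and 1.23 when it was dropped. The nominal 95% interval covered the adjusted HR in 61% and the routine-care HR (1.25) in 53%. With either model fixed in advance, coverage of its own target was 93-97%.

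**Step 6, can FFR itself be lost?** Its univariate SE is 1/√(2.56 D): 0.057 at 120 events and 0.033 at 360. At FFR HR 1.3 and treatment HR 0.6, z = 0.157/0.057 = 2.8 at 120 events (about 13% fail) and 4.8 at 360 (almost none). In simulation at 120 events and treatment HR 0.5-0.6, FFR failed in 16-36% of studies at FFR HR 1.3 and in 64-81% at 1.2. At 360 events it failed in 28-70% at FFR HR 1.2 with those treatment HRs, and otherwise in 0-4%.

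**Weaker guidance (70% and 15% treated).** The FFR HR without management is 1.22 at treatment HR 0.6 and 1.26 at 0.8, against 1.30. Management fails in 84% and 70% of studies at treatment HR 0.6 (120 and 360 events), and in 78% and 59% at 0.8.

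**The case against.** The strongest objection is that the protocol lists no candidate variables. It never says index FFR or management will be screened. An analyst could keep each exposure in its own model and screen only covariates, and a statistical analysis plan may say so. That stands, and it is why the point is conditional. But the p<0.1 rule is the only entry criterion given, and a later plan that followed it would inherit the problem.

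The strength of guidance is also assumed. The synopsis has investigators analysing index images after enrolment, so some angiography-derived values may not have guided treatment. Weaker guidance narrows the gap but does not remove it. In much of the range selection is also nearly one-sided, so the same quantity would usually be reported. In the mixed case of Step 5, failure falls to 19% at 550 events. A published table would normally list its covariates, so a careful reader could often tell which HR was shown.

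Three stronger readings are tempting and not supported:
- A reader might infer that the rule makes revascularisation look harmful. A crude treatment HR above 1, or a log-rank result towards harm ("differences between groups will be tested using the log-rank test", with no groups named), is ordinary confounding by indication. It would arise with no screening rule at all.
- A reader might infer that FFR will usually drop out of the management comparison. Step 6 confines this mainly to few events or a weak FFR effect.
- A reader might infer that one of the two FFR hazard ratios is wrong. Neither is.

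**Conclusion.** The point holds in conditional form and should be fixed. For two variables linked as Sections 6 and 8 describe, univariate p<0.1 is a poor sole criterion. If management is screened by it, the FFR-VOCE HR can be either of two quantities. The gap is about 1.17 against 1.30 at treatment HR 0.6 and 1.24 against 1.30 at 0.8, with none if treatment has no effect. At 0.6, management is dropped in over four-fifths of studies even at 550 events. At 0.8, more events largely cure this under strong guidance.

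The mechanism rests on the protocol's own description. The sizes rest on the assumed FFR distribution, guidance strength and hazard ratios, and on a single vessel per subject.

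**What to change.** Replace the p<0.1 sentence in Section 12 with:

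> Index FFR and index management (target vessel revascularised or deferred) are exempt from univariate screening. For the primary objective, the FFR-VOCE association is reported without management (risk under routine care) and also with management in the model, each labelled. The conservative-versus-invasive comparison is always adjusted for index FFR and for clinical confounders chosen in advance on subject-matter grounds. Univariate p<0.1 screening is used only for exploratory predictor searches.

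The cost is wording and one extra model. FFR is already recorded and the treated-versus-deferred comparison is already planned. With management in the model, the standard error of the FFR log HR rises from about 0.058 to 0.078 at 120 events and from 0.033 to 0.045 at 360 (90%/5% guidance). Overlap is thin, at about 77 of 1,100 vessels. Unmeasured confounding remains: with an assumed unmeasured severity marker, the model with both variables forced in gave a treatment HR of 0.64-0.65 when the truth was 0.6, and 1.07 when it was 1.0.
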